6.8.4.15 Change from Baseline in Patient-reported Satiety as Measured by The PSDD-NRS (Substudy)

Change from Baseline to Week 24 in PSDD-NRS will be analyzed using an ANCOVA model fitted for treatment, BMI at Screening ($<25 \text{ kg/m}^2$, $\geq 25 \text{ kg/m}^2$), Week -2 A1C ($\leq 9\%$, $>9\%$), and use of CSII at Screening (Yes, No), as fixed categorical effects, and Baseline PSDD-NRS as a covariate. Descriptive statistics and tests for group differences will be summarized.

6.8.5 Subgroup Analyses

Subgroup analyses of the efficacy variables will be performed for the different levels of Baseline characteristics and the randomization stratification factors. Of particular interest are the subgroup analyses of the primary efficacy endpoint and the first secondary efficacy endpoint (ie, change from Baseline to Week 24 in A1C) by:

- Age at diagnosis (<18 years, ≥ 18 years)
- Age at study entry (<75 years, ≥ 75 years)
- Sex (Male, Female)
- Race (American Indian or Alaska Native, Asian, Black or African American, Native Hawaiian or other Pacific Islander, White, other)
- Stratification for BMI categories ($<25 \text{ kg/m}^2$, $\geq 25 \text{ kg/m}^2$)
- Stratification for use of CSII (Yes, No)
- Stratification categories of Week -2 A1C ($\leq 9\%$, $>9\%$)
- Week -2 A1C ($<7.7\%$, $\geq 7.7\%$)
- Week -2 A1C ($\leq 8.5\%$, $>8.5\%$)
- Baseline eGFR status (≥ 45 to $<60 \text{ mL/min/1.73 m}^2$, $\geq 60 \text{ mL/min/1.73 m}^2$)

For the primary efficacy endpoint, the CMH test will be stratified by BMI at Screening ($<25 \text{ kg/m}^2$, $\geq 25 \text{ kg/m}^2$; excluded if it is a subgroup variable), Week -2 A1C ($\leq 9\%$, $>9\%$; excluded if it is a subgroup variable), and use of CSII at Screening (Yes, No; excluded if it is a subgroup variable).

For the change from Baseline to Week 24 in A1C, the MMRM model will have treatment, BMI at Screening ($<25 \text{ kg/m}^2$, $\geq 25 \text{ kg/m}^2$; excluded if it is a subgroup variable), Week -2 A1C ($\leq 9\%$, $>9\%$; excluded if it is a subgroup variable), use of CSII at Screening (Yes, No; excluded if it is a subgroup variable), time (study week), and a treatment-by-time interaction as fixed categorical effects, and Baseline A1C-by-time interaction as a covariate.

In addition, change from Baseline in SBP (mm Hg) at Week 16 will be summarized and analyzed using MMRM statistics with the change from Baseline at Week 16 as the endpoint and Baseline SBP -by-time interaction as a covariate, for the following subgroups:

- Baseline SBP <130 mm Hg
- Baseline SBP <140 mm Hg
- Baseline SBP ≥ 140 mm Hg

All subgroup analyses will be exploratory.

6.8.6 Net Clinical Benefit

Summaries for the following net clinical benefit endpoints assessed at the end of Double-blind Treatment Period will be provided for each treatment group in the mITT population:

- A1C at Week 24 <7.0% and SH
- A1C at Week 24 <7.0% and no SH
- A1C at Week 24 <7.0% and DKA
- A1C at Week 24 <7.0% and no DKA
- A1C at Week 24 <7.0% and no weight gain
- A1C at Week 24 <7.0% and weight gain >5%
- A1C at Week 24 <7.0% and weight loss >5%
- A1C at Week 24 <7.0% and bolus insulin reduction $\geq 20\%$
- A1C at Week 24 <7.0% and bolus insulin reduction $\geq 30\%$
- A1C at Week 24 <7.0% and basal (or non-bolus) insulin reduction $\geq 20\%$
- A1C at Week 24 <7.0% and basal (or non-bolus) insulin reduction $\geq 30\%$
- A1C at Week 24 <7.0% and total insulin reduction $\geq 20\%$
- A1C at Week 24 <7.0% and total insulin reduction $\geq 30\%$
- A1C at Week 24 <7.0% and no SH and no weight gain
- A1C at Week 24 <7.0% and no SH and no DKA and no weight gain

Only positively adjudicated SH and DKA will be included in these summaries, and the cut-off dates for their inclusion are defined in [Section 6.9.2](#). Similar summaries will be presented for other net clinical benefit measures at Week 24: A1C reduction of at least 0.3%, 0.4%, and 0.5%, with the associated SH, DKA, weight gain, and insulin reduction benefit categories. Exceptions are the summaries for A1C reduction of at least 0.4% and no weight gain; A1C reduction of at least 0.5% and no SH; and A1C reduction of at least 3% and bolus insulin reduction $\geq 20\%$, as these are either identical or very similar to 3 other efficacy endpoints (see [Section 6.8.4.4](#) to [Section 6.8.4.6](#)).

6.9 Safety

6.9.1 Adverse Events

All AEs recorded on the eCRF will be coded using the MedDRA dictionary Version 17.1 (or a later version if updated during the study) and classified as TEAEs as follows:

- TEAEs are events with start date on or after the date of first dose of double-blind study treatment and up to 30 days after date of last dose of double-blind study treatment. Some AEs may be attributed to the long-term effects of study drug and will be included in the analysis of TEAEs even if the onset is more than 30 days after the last dose of study drug.

All AE data will be listed by treatment group. Treatment-emergence status will be flagged in the listing. In addition, corresponding listings of SAEs, AEs leading to discontinuation of double-blind study treatment and AEs resulting in death will be produced.

Summary of TEAEs will be presented by treatment group for the Safety population.

The relationship between an AE and study treatment is assessed as definitely, probably, possibly, unlikely, or not related. A treatment-related AE is an AE considered by the Investigator as definitely, possibly, or probably related to treatment or with unknown/missing relationship to treatment.

Statistical Analysis Plan

Version: Final 1.0

Lexicon Pharmaceuticals Protocol No. LX 4211.1-312-T1DM

Date of Issue: 17 MAR 2017

Covance Study ID: 000000145143

An overview table will summarize the number and percentage of patients with at least 1 of the following TEAEs, where patients with more than 1 TEAE in a particular category are counted only once in that category:

- Any TEAE
- Drug-related TEAE
- Severe drug-related TEAE
- Treatment-emergent SAE
- Treatment-emergent, Drug-related SAE
- TEAE leading to study drug discontinuation
- Drug-related TEAE leading to study drug discontinuation
- TEAE leading to death

The number and percentage of patients reporting each AE will be summarized by SOC and PT for the Safety population. Tables will be sorted alphabetically by SOC. PTs will be sorted by descending overall total. The following summaries will be produced:

- TEAEs by SOC and PT
- TEAEs by PT
- TEAEs reported by at least 5% of patients in any treatment group, by SOC and PT
- TEAEs related to treatment, by SOC and PT
- TEAEs related to treatment, by PT
- TEAEs by relationship to treatment, by SOC and PT
- TEAEs by severity, by SOC and PT
- TEAEs related to treatment by severity, by SOC and PT
- TEAEs causing discontinuation from treatment, by SOC and PT
- TEAEs related to treatment causing discontinuation from treatment, by SOC and PT
- Treatment-emergent SAEs, by SOC and PT
- Treatment-emergent SAEs related to treatment, by SOC and PT
- TEAEs leading to death, by SOC and PT
- SAEs during Screening or Run-in Period leading to death, by SOC and PT

In the above summaries, patients with more than 1 AE within a particular SOC are counted only once for that SOC. Similarly, patients with more than 1 AE within a particular PT are counted only once for that PT. For summaries by maximum severity, patients with multiple AEs within a particular SOC or PT will be counted under the category of their most severe AE within that SOC or PT. In a similar manner, summaries prepared by drug relationship will select the event with the greatest degree of relationship when a patient reports multiple occurrences of the same event.

No statistical comparisons of AEs between treatment groups will be performed.

6.9.2 Events of Special Interest

Events of special interest will be captured from first dose of double-blind study drug until 30 days after last dose of study drug.

EOSIs are:

- Hypoglycemia

Statistical Analysis Plan

Version: Final 1.0

Lexicon Pharmaceuticals Protocol No. LX 4211.1-312-T1DM

Date of Issue: 17 MAR 2017

Covance Study ID: 000000145143

- DKA (including all events of metabolic acidosis)
- Volume depletion
- Myocardial infraction/hospitalization for unstable angina
- Stroke
- Hospitalization for heart failure
- Coronary revascularization
- Genital mycotic infections
- Urinary tract infections
- Diarrhea
- Pancreatitis
- Bone fractures
- Venous thrombotic events
- DILIs
- Renal events
- Malignancies of special interest (breast, bladder, renal cell, Leydig cell, thyroid, pancreatic, and prostate)
- Amputations

Based on an Information Request sent by FDA, amputations are to be added as an EOSI. This request came during the ongoing conduct of the study and methods for identifying this event will differ from those planned at the start of the study for the other listed EOSIs. Amputations will be identified as follows: The sponsor will collect all necessary data for patients who might experience amputation while participating in the study. A list of PTs will be created to identify events which may lead to amputation or which may be associated with amputations, to include amputation and conditions such as extremity ulcers, necrosis, extremity infections, etc. This predefined list of PTs will be utilized to search the database to identify the reported events of amputation and relevant events that could result in a treatment requiring amputation. Once those events are identified, sites will be queried for additional details if necessary. This information will be processed in a manner to categorize amputations as an EOSI and analyzed as the other EOSIs listed in this section.

Other AEs may be determined to be of special interest. EOSIs will be captured from first dose of double-blind study drug until 30 days after last dose of study drug. The following EOSIs may be attributed to the long-term effects of study drug: CV events (including death), bone fractures, venous thrombotic events, DILIs, and malignancies. In case any of these events is spontaneously reported by a patient, the event may be included in the analysis even if the onset is 30 days after last dose of study drug. Other EOSIs, excluding hypoglycemic events, will be included in the analysis if the onset is within 30 days of last dose of study drug. For a hypoglycemic event, the date of the last dose of double-blind study drug will be the cut-off date, regardless of the time of the hypoglycemic event; that is, a hypoglycemic event that occurs on the same day as the day of the last dose of double-blind study drug will be included in the analysis, even if it occurs at a time later than the last dose.

Events of special interest that will require adjudication by CEC are: MACE and specific CV events, DILIs, DKA (including all events of metabolic acidosis), and SH; EOSIs of SH, DKA, and CV events, if reported prior to randomization as SAEs, will be adjudicated as well.

An overall summary of number and percentage of patients with any Investigator-determined EOSIs will be presented by treatment group and overall for the Safety population. An overall summary of positively

Statistical Analysis Plan

Version: Final 1.0

Lexicon Pharmaceuticals Protocol No. LX 4211.1-312-T1DM

Date of Issue: 17 MAR 2017

Covance Study ID: 000000145143

adjudicated EOSIs will also be presented by treatment group. The summaries of Investigator-determined and positively adjudicated EOSIs will also be presented by use of CSII at Screening (Yes, NO).

Additional overall summaries will be presented for Investigator-determined EOSIs and positively adjudicated EOSIs, separately, for each of 3 time periods described as follows:

- EOSIs which start on or after the date and time of first dose of double-blind study drug and up to 30 days after the date of last dose
- EOSIs which start on or after the date and time of first dose of double-blind study drug and up to and including the date of last dose
- EOSIs which start after the date of last dose and up to 30 days after the date of last dose.

If the start time of an EOSI and/or the time of first dose of double-blind study drug is missing, then only the dates will be compared in determining the inclusion of the EOSI in the analysis for the time period of interest.

For the first and third time periods above, hypoglycemic events with onset after the date of last dose and up to 30 days after the date of last dose will be included.

Incidence rates by SOC and PT will be presented for all Investigator-determined EOSIs, those classified as serious, and those leading to study drug discontinuation.

Incidence rates by SOC and PT will be presented for all positively adjudicated EOSIs, those classified as serious, and those leading to study drug discontinuation.

Bar charts will be presented to show the incidence rates of positively adjudicated DKA and SH events, respectively, by time intervals for each treatment group.

Figures displaying recurrent events of positively adjudicated DKA or SH events by time of onset during treatment and by patient will be presented for each treatment group.

A by-patient listing of all EOSIs will be provided.

6.9.3 Death

The number and percentage of deaths, and associated primary cause of death (investigator-reported and positively adjudicated), will be summarized by treatment group and overall for the Safety population.

6.9.4 Hypoglycemic Events

Hypoglycemic events will be categorized as either (1) SH or (2) documented hypoglycemia. An episode may meet criteria for both categories. Hypoglycemic events will be classified as SH, documented symptomatic hypoglycemia, or documented asymptomatic hypoglycemia per the following definitions:

1. SH has occurred if the answer is yes to any of the following 3 questions:
 - a) Did the patient have an episode of suspected hypoglycemia treated with any form of carbohydrate or with glucagon that required the assistance of others to treat?
 - b) Did the patient lose consciousness during the episode?
 - c) Did the patient have a seizure during the episode?

Statistical Analysis Plan

Version: Final 1.0

Lexicon Pharmaceuticals Protocol No. LX 4211.1-312-T1DM

Date of Issue: 17 MAR 2017

Covance Study ID: 000000145143

2. Documented hypoglycemia: documented hypoglycemia will be defined as symptomatic or asymptomatic based on the following 2 definitions:
 - a) Documented symptomatic hypoglycemia: An event during which typical symptoms of hypoglycemia are accompanied by a concurrent fingerstick (SMBG) or venous glucose result of ≤ 70 mg/dL [3.9 mmol/L].
 - b) Documented asymptomatic hypoglycemia: An event not accompanied by typical symptoms of hypoglycemia but with a measured fingerstick (SMBG) or venous glucose result of ≤ 70 mg/dL [3.9 mmol/L].

Severe and documented hypoglycemia will be further characterized as follows:

- Nocturnal hypoglycemia defined by the time of day: any hypoglycemia that occurs between 00:00 and 05:59, regardless of whether the patient was awake or woke up because of the event;
- Diurnal hypoglycemia defined by the time of day: any hypoglycemia that occurs between 06:00 to 23:59.

SH will be further characterized as:

- Nocturnal hypoglycemia by sleep status: hypoglycemia that wakes the patient from sleep after having gone to bed in the evening and before getting up in the morning before administration of any insulin.

Hypoglycemia will be summarized as the incidence of patients (%) with at least 1 hypoglycemic event, number of hypoglycemic events per patient per year of exposure, and the number of hypoglycemic events per patient per day, by treatment group, separately for the Baseline Period (ie., 2-week placebo Run-in Period), Double-blind Treatment Period (including only those events that occur between date and time of first dose and date of last dose of double-blind study drug) and Follow-up Period (including only those events that occur after the date of last dose of double-blind study drug and on or before the 30-Day Follow-up). The incidence rate of nocturnal hypoglycemic events by time, nocturnal hypoglycemic events by sleep status, and diurnal hypoglycemic events will be presented. Similarly, total documented hypoglycemia (symptomatic and asymptomatic), documented symptomatic hypoglycemia, documented asymptomatic hypoglycemia, total hypoglycemic events (ie, SH or documented hypoglycemia), SH events, and positively adjudicated SH events will be summarized.

Incidence rates of positively adjudicated SH events by treatment group and use of CSII at Screening (Yes, No) will be presented for the Double-blind Treatment Period.

Change from Baseline in hypoglycemic events calculated as a daily average over the week prior to the visit will be analyzed as a continuous variable as described in [Section 6.8.4.12](#). Since these data also serve as a measure of safety, additional analyses will be conducted. The first analysis of hypoglycemic events will be conducted using CMH tests stratified by the randomization factors at each clinic visit. These tests will provide inferential and descriptive summaries of the relative risk estimate for each of the 2 hypoglycemic event definitions: ≤ 70 mg/dL and ≤ 55 mg/dL by SMBG. The patient incidence of these hypoglycemic events will be counted over the week prior to the scheduled clinic visit used in the analysis. The second analysis of these data will examine the relative risk for each of the hypoglycemic event definitions over the entire Double-blind Treatment Period by use of a generalized linear model (GLM). The GLM will include fixed, categorical effects of treatment; BMI at Screening (< 25 kg/m², ≥ 25 kg/m²), Week -2 A1C ($\leq 9\%$, $> 9\%$), use of CSII at Screening (Yes, No), and an offset term for ~~treatment duration~~

Statistical Analysis Plan

Version: Final 1.0

Lexicon Pharmaceuticals Protocol No. LX 4211.1-312-T1DM

Date of Issue: 17 MAR 2017

Covance Study ID: 000000145143

(natural logarithm of the treatment duration). The event rates will be modeled as a negative binomial process.

Kaplan-Meier plots of cumulative percentage of patients with the following categories of hypoglycemic events will be presented by treatment group:

- SH
- Documented hypoglycemia
- Nocturnal SH by time of day
- Diurnal SH by time of day
- Nocturnal SH by sleep status
- Nocturnal documented hypoglycemia by time of day
- Diurnal documented hypoglycemia by time of day

Patient listings for SH events (including hypoglycemic events reported as SAEs) reported by the Investigator and adjudicated by the CEC will be provided.

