5.1.2 Single-blind Placebo Run-in Period

Patients will begin the single-blind placebo Run-in Period at Week -2.

At the beginning of the single-blind placebo Run-in Period, patients electing to participate in the satiety substudy will receive packets of satiety daily diaries. The patients will be instructed to complete the paper diary each day before the first meal of the day for the duration of the single-blind placebo Run-in Period (14 days, ± 3 days). Patients will be reminded to bring the diaries with them on Day 1 (Baseline).

Patients will receive diet and exercise counseling according to nutritional recommendations for a healthy lifestyle consistent with American Diabetes Association (ADA)[14], the European Association for the Study of Diabetes (EASD)[15], or similar local guidelines, with a goal of weight maintenance to be followed for the study duration.

Glucose meter, BHB meter and supplies will be dispensed at the Run-in visit. Patients will also be educated on the use of the glucose meter and BHB meter provided for use during this study and use of the study diary to record insulin doses, SMBG, and hypoglycemic events (please see Section 7.6.1.3 for SMBG and insulin data required for CRF entry).

Compliance with the administration of single-blind placebo tablets and compliance with recording data in the study diary will be assessed during the single-blind placebo Run-in Period. Patients must demonstrate good compliance with placebo tablets ($\geq 80\%$) during the single-blind placebo Run-in Period to be eligible for randomization. Compliance will be calculated as specified in [Section 7.5.1](#).

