10.4.3 Safety Analyses

Safety analysis will primarily involve examination of descriptive statistics and individual patient listings for any effects of study treatment on clinical tolerability and safety. Summaries will be prepared by treatment group and, as needed, by clinic visit. These

summaries will be based on the Safety population and other subpopulations as needed. All safety data (AEs, EOSI, laboratory test results, vital signs, ECG results, and physical examinations) will be provided in listings.

The evaluation of AEs is described in [Section 10.4.3.1](#).

Vital signs, physical examination findings, laboratory results, and ECGs will be summarized descriptively at each time point. Actual and change from Baseline data will be calculated and summarized. In addition, shift table analyses will be presented for the laboratory data.

The analysis of hypoglycemic events will be conducted per the definitions provided in [Section 9.5.1](#) and methods described for binary, continuous, and other variables in [Section 10.4.1](#). Since these data also serve as a measure of safety, additional analyses will be conducted. The first analysis will be performed using CMH tests stratified by the randomization factors at each clinic visit. These tests will provide inferential and descriptive summaries of the relative risk estimate for each of the 2 hypoglycemic event definitions: ≤ 70 mg/dL and ≤ 55 mg/dL by SMBG. The patient incidence of these hypoglycemic events will be counted over the week prior to the scheduled clinic visit used in the analysis. The second analysis of these data will examine the relative risk for each of the hypoglycemic event definitions over the entire Treatment Period by use of a generalized linear model (GLM). The GLM will include fixed, categorical effects of treatment; BMI at Screening (< 25 kg/m², ≥ 25 kg/m²), Week -2 A1C ($\leq 9\%$, $> 9\%$), use of CSII at Screening (Yes, No), and an offset term for study duration. The events will be modeled as a negative binomial process.

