Dispense satiety daily diaries and review instruction for use [n]		X				X		
Collect satiety daily diaries [o]			X				X	
Laboratory/glycemic Assessments								
A1C [p]	X	X	X	X	X	X	X	
Fingerstick glucose on site	X	X	X	X	X	X	X	
Fasting plasma glucose [p]	X		X	X	X	X	X	
Fasting serum chemistry [p]	X		X	X	X	X	X	
Fasting lipid profile [p]	X		X		X		X	
BHB (central lab)	X	X	X	X	X	X	X	
BHB (point-of-care)	X	X	X	X	X	X	X	
Hematology	X		X		X		X	
Urine albumin, calcium, glucose, creatinine			X				X	
Urinalysis with microscopy	X		X				X	
Pregnancy test (serum) [q]	X							
Pregnancy test (urine) [q]			X				X	
Follicle stimulating hormone (females only) [r]	X							
Thyroid stimulating hormone [s]	X							
Fasting blood sample and random urine for storage			X				X	

A1C = hemoglobin A1C; ADA = American Diabetes Association; AE = adverse event; BHB = beta-hydroxy butyrate; BP = blood pressure; EASD = European Association for the Study of Diabetes; eCRF = electronic case report form; DKA = diabetic ketoacidosis; ECG = electrocardiogram; EOSI = Events of Special Interest; EOT = End of Treatment; EW = early withdrawal; IXRS = Interactive Voice/Web Response System; SAE = serious adverse event; SMBG = self-monitored blood glucose; Wk = Week

- a. The duration of the single-blind placebo Run-in Period is 14 days, ± 3 days.
- b. All laboratory assessments occur prior to first dose of double-blind study drug. All visit dates will be scheduled based on the date of randomization with a ± 3 days visit window allowed.
- c. All patients will have a follow-up telephone contact 30 days after the last dose of study drug to collect information on any SAEs, any EOSI, or AEs that were ongoing at the time of the EOT/EW Visit.
- d. A complete physical examination will include, at minimum, a review of the patient's general appearance, head, eyes, ears, nose and throat, neck, heart, lungs, abdomen, back and extremities, skin, and general neurological system. A symptom related brief physical exam will only occur if the patient is experiencing symptoms or AEs. If a symptom related brief physical exam is required, it should include a review of all body systems that relate to the symptoms and/or AE the patient is experiencing.
- e. Patients should be weighed at approximately the same time of day, wearing minimal clothing, ie, no coat/shoes, using the same calibrated scale where possible.

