17. Remind patients to bring used bottles of placebo tablets to the next visit

18. Patients participating in the satiety substudy:

- a. Dispense package of satiety daily diaries
- b. Remind patients to complete the satiety daily diaries each day before the first meal of the day, for the duration of the single-blind placebo Run-in Period (14 days, ± 3 days)
- c. Remind patients to bring the satiety daily diaries to the next visit (Day1, Baseline)

24-Week Double-blind Treatment Period (Day 1 to Week 24)

Following completion of the single-blind, placebo Run-in Period, eligible patients will enter the 24-week, double-blind Treatment Period.

Note: If serum creatinine increases by $\geq 30\%$ above the baseline value during the study, then the Investigator should consider assessment of: volume status, diuretic dose, discontinuing NSAIDs, and other relevant testing including renal imaging techniques, as appropriate.

Sodium-glucose cotransporter type 2 inhibitors are associated with osmotic diuresis and volume depletion, which may lead to dizziness or hypotension, especially in the elderly. All patients will be advised to maintain proper fluid intake and to consider increasing it if they sense greater thirst, more urine production, or if they feel dizzy or faint.

Note: The collection of AEs begins after the first dose of double-blind study drug.

24-Week Double-blind Treatment Clinic Visit (Day 1)

When scheduling the visit, remind patients that they should fast and drink only water or noncaffeinated, zero-calorie beverages for at least 8 hours prior to the visit. If the patient is unable to fast as above, the scheduled “fasting” laboratory samples will still be collected, and the non-fasting status will be noted in the eCRF.

Patients should also be reminded that they are NOT to take study drug on the day of clinic visits until instructed by site staff.

Perform the following examinations and assessments and complete the appropriate eCRFs:

1. Access inclusion/exclusion criteria
2. Randomization
3. Perform symptom-related brief physical examination
4. Measure weight
5. Measure vital signs (pulse rate, BP, respiratory rate, and temperature)
6. Perform 12-lead ECG
7. Obtain fingerstick glucose by meter to supplement review of SMBG and insulin data

8. Review SMBG and make adjustment to insulin dose as needed to meet ADA/EASD guidelines
9. Record insulin dose and SMBG on eCRF
10. Review study diary and record hypoglycemic symptoms or events

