6.8.4.9 Change from Baseline in DBP

Change from Baseline in DBP will be analyzed using MMRM statistics with change from Baseline as the endpoint and Baseline DBP -by-time interaction as a covariate. Descriptive statistics and tests for group differences will be summarized by visit.

6.8.4.10 Proportion of Patients by Visit with SBP <140 mm Hg and DBP <90 mm Hg in the Subset of Patients with Baseline SBP ≥140 mm Hg or DBP ≥90 mm Hg

The frequency and percent of patients with SBP <140 mm Hg and DBP <90 mm Hg will be presented in the subset of patients with Baseline SBP ≥140 mm Hg or DBP ≥90 mm Hg, by treatment group and visit and analyzed using the methods described for binary efficacy endpoints in [Section 6.8](#), except the CMH and NRI will be applied to Week 16 instead of Week 24.

6.8.4.11 Proportion of Patients by Visit with SBP <130 mm Hg and DBP <80 mm Hg in the Subset of Patients with Baseline SBP ≥130 mm Hg or DBP ≥80 mm Hg

The frequency and percent of patients with SBP <130 mm Hg and DBP <80 mm Hg will be presented in the subset of patients with Baseline SBP ≥130 mm Hg or DBP ≥80 mm Hg, by treatment group and visit and analyzed using the methods described for binary efficacy endpoints in [Section 6.8](#), except the CMH and NRI will be applied to Week 16 instead of Week 24.

6.8.4.12 Change from Baseline by Visit in Hypoglycemic Events Calculated as a Daily Average over the Week Prior to the Visit

Change from Baseline in the following endpoints will be analyzed by visit:

- Hypoglycemic events/patient/day (≤ 70 mg/dL) by SMBG
- Hypoglycemic events/patient/day (≤ 55 mg/dL) by SMBG

Change from Baseline in hypoglycemic events, calculated as a daily average over the week prior to the visit, will be analyzed using MMRM statistics with change from Baseline as the endpoint and Baseline-

Statistical Analysis Plan

Version: Final 1.0

Lexicon Pharmaceuticals Protocol No. LX 4211.1-312-T1DM

Date of Issue: 17 MAR 2017

Covance Study ID: 000000145143

dependent variable-by-time interaction as a covariate for each of the 2 hypoglycemic event definitions: ≤ 70 mg/dL by SMBG, and ≤ 55 mg/dL by SMBG. Descriptive statistics and tests for group differences will be summarized for all visits.

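### The negative binomial model for hypoglycemia leaves out each patient's run-in event rate, which is already recorded; adding it would sharpen the rate ratio at almost no cost

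*SAP*

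**What the plan says.** Protocol 10.4.3 and SAP 6.9.4 plan two additional analyses of SMBG hypoglycemia. The second is a generalized linear model for each definition (at or below 70 mg/dL, at or below 55 mg/dL) over the whole treatment period. The SAP states: "The GLM will include fixed, categorical effects of treatment; BMI at Screening", followed by the Week -2 A1C and CSII strata and a log-duration offset. The protocol has the same covariates and adds: "The events will be modeled as a negative binomial process". Neither document includes a term for earlier hypoglycemia.

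Run-in hypoglycemia is nonetheless recorded and reported:
- Protocol 5.1.2 trains patients at the start of run-in in "use of the study diary to record insulin doses, SMBG, and hypoglycemic events".
- The Day 1 visit (Protocol Appendices A and I) includes "Review study diary and record hypoglycemic symptoms or events".
- Footnote a of the schedule states: "The duration of the single-blind placebo Run-in Period is 14 days", with a 3-day tolerance either way.
- SAP 6.9.4 tabulates hypoglycemia "separately for the Baseline Period (ie., 2-week placebo Run-in Period" and the later periods.

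For the same two definitions, the MMRM in SAP 6.8.4.12 uses the baseline "dependent variable-by-time interaction as a covariate for each of the 2 hypoglycemic event definitions".

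**The concern.** Patients differ widely in how prone they are to hypoglycemia. In a negative binomial model that variation appears as overdispersion and, unless events are rare, it dominates the standard error. A patient's own recent rate is the natural predictor of it, and here it is measured before randomization.

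The SAP uses such information elsewhere: baseline events in the MMRM, and Baseline BHB in the logistic models of SAP 6.9.5. The negative binomial model is the exception, and no reason is given. It is also the only adjusted between-group model that uses events from the whole treatment period, because the MMRM and the by-visit CMH tests use only the week before each visit.

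Lower hypoglycemia risk is part of the rationale (Protocol 3.1.1.1 and 3.7), so the interval around this ratio will be read closely. A tighter interval is equally useful if the drug raises the rate.

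**Working it through.** **The plan's own figures.** The documents state no power, rate, dispersion or precision for this model. The nearest figure is the half-width for severe hypoglycemia at 700 per group (Protocol 10.1, SAP 2.3), and it reproduces: 1.96 × √(2 × 0.1 × 0.9 / 700) + 1/700 = 0.0329, stated as 0.033.

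**Inputs from the documents.** 700 patients per group, 14 run-in days, 24 weeks (168 days) of treatment.

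**Inputs assumed, because the documents give none.** Control rate 0.03, 0.1, 0.3 or 0.5 events per day. Log-normal patient rates with frailty variance 0.5, 1 or 2. Correlation of 0.4, 0.6 or 0.8 between a patient's run-in and treatment log rates. Rate ratio 0.85. 10% of patients stop early at a random day.

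**Method.** The negative binomial model was fitted to simulated trials (8 per scenario) with and without log((run-in events + 0.5)/14). The table gives the standard error (SE) of the log rate ratio with the covariate divided by the SE without it, as a range over the three frailty variances.

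| Events/day | Correlation 0.4 | Correlation 0.6 | Correlation 0.8 |
|---|---|---|---|
| 0.03 | 0.98–0.99 | 0.96–0.99 | 0.93–0.97 |
| 0.1 | 0.97–0.98 | 0.92–0.96 | 0.85–0.91 |
| 0.3 | 0.96 | 0.89–0.92 | 0.77–0.83 |
| 0.5 | 0.94–0.96 | 0.87–0.89 | 0.74–0.80 |

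The SE therefore falls by about 1% to 26%. If each patient's rate were perfectly stable (correlation 1.0), the fall would be about 5% to 50%.

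**Check by formula.** Ignoring early stopping, Var(log rate ratio) ≈ (1/μc + 1/μt + 2κ)/700, where μc and μt are the mean events per patient on control and active treatment, and κ is the fitted dispersion. At 0.3 per day, μc = 0.3 × 168 = 50.4 and μt = 0.85 × 50.4 = 42.84. With frailty variance 1, the fitted κ without the covariate was 0.65:
- Without the covariate: √((0.0198 + 0.0233 + 1.30)/700) = 0.0438 (simulated 0.0439).
- With it, correlation 0.6, κ = 0.51: √((0.0432 + 1.02)/700) = 0.0390 (simulated 0.0393).
- With it, correlation 0.8, κ = 0.40: √((0.0432 + 0.80)/700) = 0.0347 (simulated 0.0351).

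Nearly all of the variance is the 2κ term, which is the part that the run-in rate reduces.

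**What that means for the interval.** In this middle scenario the SE ratios are 0.896 and 0.800, equivalent to 1/0.896² − 1 = 25% and 1/0.800² − 1 = 56% more patients. The 95% limits are the estimate multiplied or divided by exp(1.96 × SE), which is 1.090 without the covariate and 1.080 or 1.071 with it. For an estimate of 0.85 the interval moves from 0.78–0.93 to 0.79–0.92 or 0.79–0.91.

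**Why rare events gain little.** At 0.03 per day a 14-day run-in yields on average 0.03 × 14 = 0.42 events, so most counts are 0 or 1 and say little about the patient. At 0.3 per day it yields 4.2.

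**The case against.** The strongest reply is that little depends on this model. The protocol synopsis calls the safety analysis descriptive, the model is the second of two additional analyses, and these endpoints lie outside the testing hierarchy in SAP 6.8. Severe hypoglycemia, the component of the primary endpoint, is not what it analyses. Without the covariate the SE is already about 0.034 to 0.064, giving limits within a factor of about 1.07 to 1.13. The MMRM also supplies baseline-adjusted comparisons at each visit. All of this stands and limits the importance of the point. It does not remove the gain, and the MMRM's one-week windows do not replace a whole-period ratio.

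The run-in count may also predict less well than simulated. Protocol 8.2.2 specifies 5-point SMBG profiles for the treatment period only. Insulin is changed from Day 1 (Protocol 7.6.1.4). Protocol 9.5 starts capture of events of special interest, which include hypoglycemia, at the first double-blind dose. The diary training, the Day 1 review and the SAP's Baseline Period table show that run-in events are recorded, but their completeness should be confirmed. The simulation also gave no prognostic role to the strata already in the model, which may absorb some of the variation.

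A reader might infer that the ratios are much less precise than they could be, with intervals 12% to 25% too wide. A simulation with gamma overdispersion 0.5 to 1.5 and period drift of log-SD 0.4 to 0.8 does give a variance reduction of 22% to 43%. But those inputs imply run-in/treatment correlations of about 0.71 (√(0.645/(0.645 + 0.64))) to 0.97 (√(3.06/(3.06 + 0.16))), and nothing in the documents supports values that high over lower ones. A reader might also infer bias. There is none: the omitted variable precedes randomization.

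**Conclusion.** The omission is confirmed in both documents, and it is inconsistent with the SAP's own MMRM of the same events. The cost is precision only. The SE of the log rate ratio would be about 1% to 26% lower under the assumed rates (0.03 to 0.5 per day) and correlations (0.4 to 0.8). For rare events, as might apply at or below 55 mg/dL, the gain is about 1% to 7%; with very stable patient rates it is more than 26%. The direction is secure. The size is not, because the event rate, dispersion and correlation are all assumed. No confirmatory conclusion is affected. This is a minor point, worth making because the improvement is nearly free.

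**What to change.** Before unblinding, amend SAP 6.9.4 so that each of the two negative binomial models includes log((run-in events + 0.5)/run-in days recorded) as a covariate, counted with the same glucose definition as the outcome. Using the days actually recorded allows for the variable run-in length.

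State a rule that keeps patients without usable run-in data in the model, for example the overall mean of the covariate plus a missing-data indicator. Confirm under blind that run-in events were captured consistently.

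The cost is one derived covariate and one missing-data rule in two models, with no new data collection. If the run-in count proves a weak predictor, the loss is about one degree of freedom among 1400 patients. With a log link the rate ratio keeps its interpretation. Adding the term after unblinding would look data-driven, so timing matters more than effort.
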